1.4. Qualitative and Implementation Objectives and Outcomes

Additional outcomes of this study are to:

- Elicit perspectives from patients, CRAs, and clinicians about effort, benefits, and burden of patient self-reporting of symptoms with alerts and reports to clinicians.
- Identify barriers, facilitators, and strategies used by practices to integrate PROs into clinical workflow through interviews, questionnaires, and selected site visits, including impact of patient characteristics such as race, ethnicity, computer experience, or educational background.
- Obtain perspectives of stakeholders about PROs through debriefings at study completion.
- Evaluate financial impact of patient self-reporting.

2. Patient Selection and Population

2.1. Inclusion and Exclusion Eligibility Criteria

Inclusion Criteria:

1. Adults (21+) with metastatic cancer of any type (EXCEPT leukemia or indolent [slow growing] lymphoma)
2. Receiving outpatient systemic cancer treatment for non-curative/palliative intent, including chemotherapy, targeted therapy, or immunotherapy.
3. Enrolled at any point in their treatment trajectory, meaning during any line of treatment, and at any point during a course or cycle of treatment.
4. Can understand English, Spanish, and/or Mandarin Chinese.

Exclusion Criteria:

1. Cognitive deficits that would preclude understanding of consent form and/or questionnaires.
2. Current participation in a therapeutic clinical trial (because these often involve PRO questionnaires and intensive monitoring).
3. Patients being treated with curative intent (e.g., adjuvant chemotherapy for breast, lung, or ovarian cancer; primary curative therapy for testis cancer or lymphoma).
4. Receiving hormonal therapy only (e.g., tamoxifen or aromatase inhibitors in breast cancer; androgen deprivation therapy in prostate cancer; or octreotide in neuroendocrine cancers; ibamacare/palbociclib)
5. Indolent lymphomas (due to their prolonged time courses that may be minimally symptomatic).
6. Leukemias (time courses inconsistent with other tumor types in chronic and acute leukemias).
7. Does not understand English, Spanish, or Mandarin Chinese.

3. Site Enrollment and Responsibilities

3.1. Study Site Arm Assignment and Registration (Form C1)

Patients will be enrolled from up to 50 oncology clinical practice sites across the U.S. Sites (+/- 5 sites) will be contracted by AFT and adhere to the AFT central IRB and procedures for registration and data management (including outcomes data capture in the PRO-Core clinical trial software system, which will be used for participant registration and all study forms for this trial).

The unit of randomization for this trial is the oncology practice site. Each site will be assigned as either a “Control Arm Site” or as an “Intervention Arm Site”. Arm assignments will be provided to sites by the UNC study coordinating team by email to the lead CRA following site’s local IRB approval and before the site’s initiation/startup training webinar with UNC.

CRAs will complete the Site Registration Characteristics Form (Form C1) prior to the site initiation/startup training webinar with UNC.

3.2. Site Enrollment Required Documentation

Each site must submit the below required essential documents to the Alliance through the AFT electronic Trial Master File, accessible via the AFT website, <https://alliancefoundationtrials.org/>

- IRB Documents/ Approvals (Protocol, Informed Consent Form (ICF), Participant Materials, etc.)
- Institutional Informed Consent Form (a ‘model’ consent form will be provided to sites)
- Investigator FDA Form 1572
- Curriculum Vitae (CV) from site Principal Investigator

- Documentation of ICH Good Clinical Practice (ICH/GCP) training from site Principal Investigator
- Site CRA and site Nurse Champion study training certificates (provided by UNC after the site initiation webinar)

3.3. Site Role Requirements

3.3.1 Clinical Research Associate (CRA)

Each site will allocate effort from at least one Clinical Research Associate (CRA) to oversee processes for this trial.

CRAs at ALL SITES will:

- Oversee regulatory and logistical processes for the trial at their site
- Complete the “Site Registration Characteristics Form” (Form C1) prior to the site initiation/startup training webinar with UNC
- Participate in the site initiation/startup training webinar with UNC (and provide a training certificate from this webinar to AFT)
- Screen for eligible patients
- Oversee informed consent
- Submit clinical data at baseline and off-study for participants, and abstract date of death information at 18 and 24 months, and possibly later, per the UNC study team
- Ensure completion of outcomes questionnaires by participants or their caregivers at baseline, month 1, 3, 6, 9, and 12/off-study
- Participate in teleconferences and individual telephone calls with the central data management team as needed to discuss accrual, retention, and compliance with forms.

CRAs at INTERVENTION SITES ONLY will additionally:

- Participate in training for PRO (“patient-reported outcome”) weekly survey system
- Teach patients to use the PRO system
- Forward PRO system email alerts to nurses/clinicians
- Print PRO reports for clinicians at patient visits
- Follow up with nurses after alerts (within 72 hours) and enter information about their responses to alerts in a study form
- Complete the “CRA Perspectives Survey” form after at least 6 months of site participation
- Facilitate nurse completion of the “Nurse Perspectives Survey” and “Physician Response Survey” forms after at least 6 months of site participation
- Participate in brief telephone or in-person debriefings with the study team to discuss PRO interventions and workflow.
- Contact patients after 48 hours of initial survey email/text/call to remind them to complete surveys. This will be done in coordination with the UNC Coordinator. (CRAs will be asked to avoid contacting patients more than three times each week)

3.3.2 Site Nurse Champion

Each practice site must designate a Nurse Champion prior to site initiation/startup training.

Nurse Champions at ALL SITES will:

- Participate in the site initiation/startup training webinar with UNC (the CRA will submit a training certificate for the nurse from this webinar to AFT)
- Facilitate dissemination of the standardized symptom management pathways to site nurses who care for study participants

Nurse Champions at INTERVENTION SITES ONLY will additionally:

- Work with UNC to figure out the optimal way to integrate PROs into the practice
- Be a resource for other clinicians and participants
- Receive a copy of email alerts being sent to clinical nurses from the CRA at that site, as an added Quality Assurance (QA) step
- Complete, or designate a participating clinical nurse with patient(s) in the study to complete, the “Nurse Perspectives Survey” form after at least 6 months of site participation; may also participate in brief telephone or in-person debriefings to discuss PROinterventions.

3.4. Data Management Software (“PRO-Core”)

All data entry for this study will be conducted through the online PRO-Core data management system (<https://pro.unc.edu>). This includes all forms that are completed by site CRAs, and patient questionnaires. As described in the following sections, CRAs and other site staff, including the designated Nurse Champion, will be trained to use the PRO-Core system during the site initiation/startup webinar. For intervention sites only, during this webinar, site staff will also be trained how to teach patients to use the PRO weekly symptom survey system.

3.5. Site Initiation/Startup Webinar with PRO-Core Software Training

Each site will undergo a required startup meeting webinar set up by the UNC Coordinator/team, attended by the site PI, CRA(s), and designated Nurse Champion at a minimum, but optimally including all clinical nurses who might be clinically responsible for patient participants. Following training, the UNC Coordinator (not the site CRA) will complete the “Site Training Form” (Form UNC-1). Training will include instructions for using the PRO-Core software for patient registration and completion of forms. The UNC Coordinator will provide training certificates for the CRA to provide to AFT, once both the CRA and Nurse Champion are trained. Refresher trainings and trainings for new site personnel will be available at any time during the trial through the UNC coordinating center.

FOR SITES ASSIGNED TO INTERVENTION ARM ONLY:

- The CRA(s) and Nurse Champion will also be trained to use the PRO (“patient-reported outcome”) weekly survey software, which is integrated with the PRO-Core data management software being used for this study. This training takes approximately 30 minutes. CRAs will be trained how to:
 - Register a patient into the PRO software
 - Select the patient’s preferred mode of completing the Weekly Survey (online or automated telephone)
 - Designate the clinical nurse(s) and oncologist responsible for the care of that patient
 - Teach patients to use the PRO system from home (online or automated telephone) (typically less than 10 minutes to train patients)
 - For patients who choose the automated telephone system, how to set/reset a PIN
- Site personnel will be familiarized with the automated email alerts that will go to the site CRA when a patient reports concerning or worsening symptoms. The automated emails must be forwarded by the CRA to the appropriate clinical nurse(s) caring for the participant with a CC to the site’s Nurse Champion.
- CRAs will be oriented to the wallet-sized quick-reference information cards for patient participants including instructions how to use the PRO system. These will be provided to CRAs by the UNC coordinating center.

4. Patient Recruitment and Enrollment

4.1. Identify/Select/Recruit Participants

Site CRAs will work with clinical nurses and oncologists at their practice sites to identify eligible patients. To identify potentially eligible patients, CRAs can review clinical documentation such as the patient's chart in the electronic medical record, clinical schedules, or ask clinical staff about potential eligible patients through a limited waiver of authorization from the IRB. Potential patient participants may be approached and invited to be in the study by site CRAs or designated clinical staff. All eligible patients should be approached consecutively, except when "purposeful enrollment" for specific target populations is directed for sites by the UNC study team, as described below. Patients who agree to participate will review and sign the Informed Consent Form after the study is explained.

4.2. Documentation of Refusals/Ineligibility (Form C2)

Patient refusals or ineligibility to participate and reasons for refusal will be entered into the "Patient Refusal to Participate/Ineligibility Form" (Form C2).

4.3. Purposeful Enrollment

We will use purposeful enrollment to enrich the sample for historically underserved populations. This will be managed through central monitoring of accrual by UNC, with close communication with site CRAs. Enrollment methods may include restricting enrollment to specific populations after sites reach a certain number of participants (e.g. 50 or 20), and/or recruiting sites with varying patient demographics, and/or training sites to approach potential patients regardless of race, ethnicity, age, education level, or any other patient level characteristics.

4.4. Participant Registration and Study ID (Form C3)

Prior to registering the patient, site staff should verify the following:

- All eligibility criteria have been met within the protocol stated timeframes.
- The patient has signed an appropriate consent form and HIPAA authorization form (if applicable at your site)
- The patient has been informed about the \$150 in gift cards (\$75 at baseline and \$75 at 3 months) that will be sent to them by UNC for participating

After written informed consent has been obtained, the study site CRA will register the patient in the PRO-Core software system by completing the "Patient Registration Form" (Form C3). In this form, the CRA will assign a unique Study ID for the patient using the three-digit code assigned to their site for the study, followed by a hyphen then a three-digit consecutive number for that patient. For example, the fifth patient registered as a participant at site #123 would be 123-005. In addition, in this form the CRA will specify, on behalf of the patient, how the patient prefers to complete questionnaires for the study: online or by an automated telephone system.

Patients enrolled but who do not participate for any reason will be considered as a Screening Failure and will not be considered as enrollees.

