7.1. Statistical Tests

The principal (primary) outcome is overall survival. Overall survival will be compared between arms using a stratified log-rank test (stratified by cancer type, with a sandwich estimator to account for site clustering). Each patient will be analyzed according to his/her site's randomized assignment (intent-to-treat approach). In keeping with evolving scholarly thinking, we will not consider any specific threshold of statistical significance in deeming the intervention in this trial a success, and instead the outcome of the study will be based on interpretation of all conducted analyses taking into account both statistical and clinical significance (Wasserstein RL, Schirm AL, Lazar NA. *The American Statistician*. 2019; 73[sup1]:1-19.). Due to the potential impact of COVID on the outcomes in this trial, and potential differential impact of COVID on clusters in the two randomization arms, adjustments in analyses may be made and a sensitivity analysis will be conducted in which overall survival data are censored at March 1, 2020.

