## 3.3. Definition of populations for analyses

### 3.3.1. Modified intention-to-treat population for patient-level analysis

We will use a modified intention-to-treat (mITT) principle to define the population used for the analysis of the primary endpoint, which is based on data collected at the patient level. The mITT population will be comprised of all patients who consent to participate and are registered through UNC by any randomized practice. We will exclude any patient who discontinues their cancer treatment on or prior to their date of registration. Patients will be analyzed according to the practice in which they are registered, and practices will be analyzed according to the intervention group to which they were randomized. All available data will be

included in each analysis. The number of patients included in a given analysis will depend on data availability (e.g., analysis of EORTC QLQ-C30 at 12 months will include all patients who completed the necessary EORTC QLQ-C30 items to produce each scale score at 12 months).

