### 3.5.2. Data set for primary endpoint

For the main analysis of the primary endpoint, the mITT population defined in SAP Section 3.3.1 will be used.

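### Protocol 4.4 turns enrolled non-participants into screening failures, which conflicts with the intent-to-treat and mITT sets and could bias overall survival in either direction

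*Protocol*

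**What the plan says.** Protocol 4.4 gives the order of events: "After written informed consent has been obtained, the study site CRA will register the patient in the PRO-Core software system". On that form the patient receives a Study ID made of the site code and a consecutive number. The section then ends: "Patients enrolled but who do not participate for any reason will be considered as a Screening Failure and will not be considered as enrollees". It does not say what counts as participating, or by when.

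For the analysis, Protocol 7.1 states an intent-to-treat approach by the site's randomized assignment. SAP 3.3.1 is more specific: "The mITT population will be comprised of all patients who consent to participate and are registered through UNC by any randomized practice". It names one exclusion: "We will exclude any patient who discontinues their cancer treatment on or prior to their date of registration". SAP 3.5.2 carries this set to overall survival: "For the main analysis of the primary endpoint, the mITT population defined in SAP Section 3.3.1 will be used". SAP Section 4, on departures from the protocol, does not mention the sentence in 4.4.

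On knowledge of arm, Protocol 3.1 says: "Arm assignments will be provided to sites by the UNC study coordinating team by email to the lead CRA". This happens before the startup webinar, and so before a site enrolls anyone. Under Protocol 5.1 and 5.4, intervention patients are also trained at baseline for weekly surveys and then asked to complete them. Control patients have only the periodic outcomes questionnaires.

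**The concern.** A consented, registered patient who never takes part belongs to the SAP population but is not an enrollee under Protocol 4.4. The SAP can analyse only patients who reach the dataset. If a site follows 4.4 literally, the Date of Death Form (at off-study, 18 and 24 months, Protocol 5.5.2) and the death-database linkage (SAP 3.1.6) may never be applied to that patient, and the CONSORT count may omit them.

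That would be an exclusion made after entry, in an open cluster trial, by staff who know the arm. What a patient must do at the start is somewhat greater in the intervention arm, and patients who do not start may have a different prognosis. The covariates that SAP 3.5.3 names as examples for the primary Cox model (line of treatment and two disease intervals) do not include performance status, so adjustment might not remove such a difference. The primary endpoint is at stake.

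**Working it through.** **Step 1. Which patients does the sentence cover?**

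| Patient | Protocol 4.4 | SAP 3.3.1 |
|---|---|---|
| Consented, registered, takes part | enrollee | in mITT |
| Consented, registered, never takes part | screening failure | in mITT |
| Registered, cancer treatment already stopped by registration | not addressed | excluded |
| Consented, never registered | could be covered on a narrow reading | not in mITT |

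The second row is the conflict. Three things favour reading 4.4 as covering that row: the sentence follows registration and ID assignment; Protocol 4.5 uses the word enrolled for patients whose baseline forms come next; and refusals and ineligibility already have their own form (C2, Protocol 4.2). The narrow reading in the last row would remove the conflict, but the text does not state it.

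**Step 2. The plan's own figure.** Inputs from Protocol 7.2: 1,200 patients, 52 sites, ICC 0.001, 576 events, HR 0.76, two-sided alpha 0.05.

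- Mean cluster size m = 1200/52 = 23.08. Design effect DE = 1 + (m − 1) × 0.001 = 1.0221, an approximation to the Xie-Waksman adjustment.
- Power = Φ(√(576/DE/4) × |ln 0.76| − 1.96) = Φ(11.87 × 0.2744 − 1.96) = Φ(1.30) = 90.3%.

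The stated power of at least 90% reproduces. The present issue is one of bias and does not change it.

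**Step 3. How large could the bias be?** The documents give no non-participation rate and no prognosis for such patients, so the exclusion rates and hazard multiples are assumptions. The true HR is set to 1. A fraction f of each arm are would-be non-participants with hazard hλ; the rest have hazard λ. Survival is exponential, with λ chosen so that 576/1200 = 48% die within 730 + 42 = 772 days (the SAP 3.2.3 horizon). Some or all of the fraction f are then removed, by arm. The large-sample, unadjusted Cox log hazard ratio β solves

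∫ [d_I − (d_I + d_C) · e^β S_I / (e^β S_I + S_C)] dt = 0,

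where S and d are the retained number at risk and the death density in each arm.

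| Excluded, intervention / control | h = 1.5 | h = 2 | h = 3 |
|---|---|---|---|
| 5% / 0% | 0.98 | 0.96 | 0.94 |
| 10% / 0% | 0.96 | 0.93 | 0.89 |
| 10% / 5% | 0.98 | 0.96 | 0.94 |
| 5% / 5% | 1.00 | 1.00 | 1.00 |
| 0% / 5% | 1.02 | 1.04 | 1.06 |

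With 55% dead (576/1050, removing the 150 assumed drop-outs), the 5% / 0% row becomes 0.98, 0.96 and 0.95. The other rows are unchanged to two decimals.

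Hand check of 5% / 0% at h = 2. Put x = exp(−λT). Then 0.95(1 − x) + 0.05(1 − x²) = 0.48 gives x = 0.5325. Cumulative hazard is −ln 0.5325 = 0.630 in the intervention arm (non-participants gone) and −ln 0.52 = 0.654 in the control arm. The ratio is 0.96, as in the table.

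**Step 4. Scale.** Five percent of an arm of 600 is 30 patients. With 576/DE events, a two-sided p of 0.05 needs an HR near exp(−1.96/11.87) = 0.85. The chance of a nominally significant benefit under no effect is Φ(11.87 × (−ln HR) − 1.96). It is 2.5% without bias, 4.4% to 10.7% at 5% / 0%, and 1.3% down to 0.4% at 0% / 5% (48% dead, h from 1.5 to 3). Protocol 7.1 sets no significance threshold, so these chances are only a yardstick.

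**The case against.** The strongest reply is that the analysis population is already right. SAP 3.3.1 keeps every consented and registered patient but for one stated exclusion, and SAP 3.5.2 applies it to survival. Protocol 4.4 is a registration section: it says who counts as an enrollee, not who is analysed, and no section says that registered records are deleted. Study IDs are consecutive and Protocol 9.8 requires database changes to be documented, so a removed patient should leave a trace. All of this stands. It does not settle what a site would do with a patient whom the protocol tells it not to count.

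The plan also deals with most later non-participation elsewhere. Missed weekly surveys lead to reminders, interview completion and Forms C6 and C8 (Protocol 5.4.1 and 5.4.2), and patients expected to report stay in the adherence denominator (SAP 3.6.3). Voluntary disenrollment, hospice and death are off-study events (Protocol 6.4). The coherent reading of 4.4 is therefore patients who never start. The first outcomes questionnaire is the same in both arms and is ideally completed in clinic with help. The extra intervention training leaves some room for a difference between arms, but not much.

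A reader might infer that the rule favours the intervention because weekly reporting drives frail patients out. The documents do not support that. They do not treat a missed weekly survey as non-participation, they give no rates by arm, and exclusions concentrated in the control arm would push the hazard ratio the other way.

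**Conclusion.** The inconsistency is real. As placed, Protocol 4.4 is an undefined post-registration exclusion that conflicts with Protocol 7.1 and SAP 3.3.1. The SAP population needs no repair; the doubt is whether every registered patient reaches it with death follow-up.

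Neither the direction nor the size of any bias can be determined from the documents. At the assumed 5% versus 0%, with 1.5 to 3 times the hazard, a null HR moves to about 0.94 to 0.98 or to 1.02 to 1.06, depending on which arm loses patients. With equal exclusion of equally frail patients there is none in this model. These figures rest on exponential survival, a Cox model without the planned covariates or site effect, and exclusion rates that are purely illustrative. If no registered patient was reclassified, the effect is nil, and reporting that count closes the matter.

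**What to change.** 1. In Protocol 4.4, limit screening failure to patients who were never registered. State that every registered patient stays in the mITT population as SAP 3.3.1 defines it, with that section's treatment-discontinuation exclusion as the only one.
2. State that death follow-up and database linkage continue for these patients as far as their consent allows. Protocol 9.7 limits disclosure to what the signed consent or authorization, or the law, permits, and SAP 3.2.3 notes that linkage needs identifiers from sites, so some patients may have to be censored early.
3. Check the Form C3 registration log, including gaps in the consecutive Study IDs, against the mITT count. Restore any registered patient removed under 4.4.
4. Report the number and reasons by arm in the CONSORT diagram already planned in SAP 3.4.1, and note the reconciliation in SAP Section 4.

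The cost is a short clarification, a log check and, if anyone was removed, some site queries and linkage work. Recruitment was due to start in August 2017 with about three years of accrual, while the protocol is dated December 2020 and the SAP September 2022. On that timeline the rewording would no longer change site conduct, so steps 3 and 4 carry most of the value.
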